5.4.4 Handling of Multiplicity

Due to early termination of the study by the sponsor, the sample size is not sufficient for the hierarchical hypothesis testing. All of the secondary endpoints will be analyzed inferentially as reference only.

5.5 Safety Analysis

5.5.1 General Considerations

The safety variables to be analyzed include all AEs occurring after informed consent, all study-emergent AEs, AdreView™-emergent AEs, SAEs, vital sign data, physical examination results, clinical laboratory test data, and electrocardiographic data. All safety analyses will be performed by study arm in the safety population. All safety data will be listed by study arm and patient number.

5.5.2 Analysis of Adverse Events

All AEs occurring after informed consent were recorded on the eCRF. A study-emergent AE is defined as an AE that occurred after randomisation. An AdreView™-emergent AE is defined as an AE that occurred or worsened within 24 hours after administration of AdreView™ and in addition any AE which occurred more than 24 hours after administration of AdreView™ for which a causal relationship is assumed by the investigator. If the date of occurrence of an AE cannot be determined relative to date of randomisation, it will be assumed to be both study-emergent and AdreView™-emergent. AEs will be mapped to preferred terms and system organ class using the Medical Dictionary for Regulatory Activities (MedDRA) coding dictionary version 19.0.

All AEs will be listed by enrolment group and patient number, and AdreView™-emergent AEs/SAEs will be flagged.

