9.3 Post-Randomisation Procedures

All female patients (unless pre-menarchal, surgically sterile or post-menopausal) will undergo a serum or urine pregnancy test on the day of and prior to AdreView™ administration. AdreView™ dosing will only commence if the result is negative.

AdreView™ will be administered to all patients.

The first AdreView™ administration should be performed in the 15 (+7) days post-randomisation. Starting at 3 hours 50 minutes after administration of AdreView™, patients will undergo a 10-minute acquisition of anterior planar images of the thorax, and whenever possible these will be followed by a SPECT acquisition. Details of the acquisition and transmission of images to the Sponsor are provided in the study Imaging Manual.

Only those patients allocated to the AdreView™ arm will have the results of the scan (H/M ratio calculated on an anterior planar image obtained at 3 hours and 50 minutes for 10 minutes, and with regions placed following the standard quantification method according to the Imaging Manual) available to make a decision on the need for implantation of an ICD. In patients allocated to the SoC group, the investigator will remain blinded to the results of the AdreView™ images and any information derived from them in order not to influence the decision to implant or not implant an ICD.

Patients in the AdreView™ arm who are deemed at high-risk for all-cause and cardiovascular mortality (H/M ratio <1.6 as defined in Section 6.1) will undergo ICD device implantation. ICD implantation should be performed within 45 days of randomisation. Patients deemed to be at low risk (H/M ratio ≥ 1.6 as per Section 6.1) will continue to receive guideline-directed optimal medical therapy but will not undergo ICD implantation. In the low risk group, a second AdreView™ scan will be performed at 2 years following the first scan, or in case of early withdrawal, prior to this withdrawal being effective.

Patients randomly allocated to the SoC group will undergo ICD implantation and will be managed and followed up in accordance with internationally accepted HF guidelines. ICD implantation should be performed within 45 days of allocation to the SoC group. The results of the AdreView™ scan will remain blinded to the investigator to avoid any influence regarding patient management. AEs, SAEs and AdreView™-emergent AEs will be recorded.

All data related to primary and secondary endpoints will be collected.

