- f AdreView™ will be administered to all patients. First AdreView™ administration should be performed in the 15 (+7) days post-randomisation. For the low-risk cohort only, a second AdreView™ administration should be administered at 2 years (± 30 days) post-randomisation, unless patient withdraws prior to study termination or has already received an ICD. In this case the second AdreView™ scan will be offered before withdrawal becomes effective. Thyroid blocking should be performed before administration of AdreView™ in accordance with the Package Insert/Summary of Product Characteristics/IB and local regulations unless the patient has had a complete thyroidectomy.
- g At 3 hours 50 minutes after administration of AdreView™, patients will undergo a 10-minute acquisition of planar images, and whenever possible followed by SPECT acquisition, according to the imaging manual. Patients with LVEF 25% to 35% with an H/M ratio ≥ 1.6 will have a second AdreView™ scan at 2 years (± 30 days) post-randomisation.
- h Patients in the randomised AdreView™ group who are assessed as high risk, and patients in the SoC group according to the standard of care in each investigational site derived from the local implementation of internationally accepted HF guidelines. ICD implantation should be performed according to clinical practice and should be performed within 45 days after randomisation.
- i ICD interrogation does not need to be performed on the same day as the corresponding follow-up visit. ICD interrogation may be done remotely within ± 5 days of the corresponding follow-up visit.
- j AdreView™-emergent AEs are defined as any AE which occurs within 24 hours after administration of AdreView™, and in addition any AE which occurs more than 24 hours after administration of AdreView™ for which a causal relationship is assumed by the investigator.
- k Patients will be enrolled and followed up until sufficient endpoints have accrued (247 primary endpoint events). All patients will then attend an end-of-study visit within 1 month.

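### SAP 5.5.2 resolves uncertain AE dates against randomisation although AdreView-emergent status runs from each injection, so some partially dated AEs get the wrong AdreView-emergent flag

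*SAP*

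**What the plan says.** SAP 5.5.2 uses two anchors. For the study period: "A study-emergent AE is defined as an AE that occurred after randomisation". For the drug, there is a timing limb, "An AdreView™-emergent AE is defined as an AE that occurred or worsened within 24 hours after administration of AdreView™", and a causality limb, "any AE which occurred more than 24 hours after administration of AdreView™ for which a causal relationship is assumed by the investigator".

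The section has one rule for dates that cannot be placed, and it uses only the first anchor: "If the date of occurrence of an AE cannot be determined relative to date of randomisation, it will be assumed to be both" study-emergent and AdreView-emergent. SAP section 5 (missing data imputation) otherwise leaves missing values as missing, so no other partial-date rule for AEs applies.

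Injection and randomisation are separate events. Protocol 9.3 states: "The first AdreView™ administration should be performed in the 15 (+7) days post-randomisation". Footnote f of the schedule in SAP 2.2 adds a later exposure: "For the low-risk cohort only, a second AdreView™ administration should be administered at 2 years" after randomisation, with a window of 30 days either side.

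**The concern.** The date rule is a worst-case rule: when timing is in doubt, count the event. To do that for the AdreView-emergent category, it has to ask whether the event could fall in the 24 hours after an injection. It asks instead whether the event could precede randomisation, which is a different question once the injection is days or two years later.

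The rest of the SAP suggests that the mismatch is not deliberate. Section 5.1.3 classifies medications against the first AdreView administration and puts those with incomplete dates in both categories. Missing intensity becomes severe (5.5.2.3) and missing relationship becomes related (5.5.2.4).

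What is at stake is the AdreView-emergent AE and SAE tables. SAP 5.5.2.2 makes them part of the primary AE presentation, and 5.5.2.1 compares the arms with p-values. Both arms receive the first injection, but only the low-risk AdreView group receives the second. Any omission around the second injection therefore falls in one arm and can only lower its count.

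**Working it through.** The plan gives no figure on this point. The check asks when an AE dated only to the month, or only to the year, of an injection can be placed after randomisation. When it can, the rule does not fire.

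**Inputs.** The first injection is planned within 15 (+7) days of randomisation, so up to day 22 (Protocol 9.3; SAP 2.2, footnote f). The second is at 2 years ± 30 days: 730 − 30 = 700 to 730 + 30 = 760 days. The documents do not give the distribution of the first lag, so I assume several. Randomisation dates are taken as evenly spread over the calendar.

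**First injection, month-only date.** The rule misses the AE when the injection falls in a later calendar month than randomisation. For a lag of L days shorter than a month, that share is L divided by the mean month length of 30.4 days. For uniform lags, L is replaced by its mean.

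| Assumed lag | Arithmetic | Share of patients |
|---|---|---|
| 7 days | 7 / 30.4 | 23% |
| uniform 1–15 days | 8 / 30.4 | 26% |
| uniform 1–22 days | 11.5 / 30.4 | 38% |
| 15 days | 15 / 30.4 | 49% |
| 22 days | 22 / 30.4 | 72% |

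Counting over every randomisation day in an illustrative three-year calendar (2016–2018) gives the same percentages.

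**First injection, year-only date.** The rule misses the AE only when the calendar year changes in between: 15 / 365 = 4% to 22 / 365 = 6%.

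**Second injection.** A lag of 700 to 760 days always puts the injection in a later calendar year than randomisation. A month-only or year-only date is then certainly after randomisation, so the rule fires in 0% of cases.

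**Both errors in one patient (illustration).** Randomised on 20 January and injected 15 days later, on 4 February:

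- An AE dated only January might precede randomisation. The rule fires and flags it as AdreView-emergent, although its latest possible date, 31 January, is before dosing.
- An AE dated only February follows randomisation. The rule does not fire, although the AE may have begun on 4 or 5 February. If not assessed as related, it is not flagged.

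**What is still captured.** A wholly undated AE cannot be placed against randomisation, so the rule flags it whichever injection it followed. An AE assessed as related qualifies through the causality limb without needing a date within 24 hours. One with missing relationship is imputed as related (5.5.2.4).

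**The case against.** The strongest reply is that little is left once the rest of the SAP is read. Related AEs count whatever their date, and wholly undated AEs are always flagged. The relationship field in 5.5.2.4 also records whether an AE came before or after AdreView, so an AE on the day of the first injection marked as after it lies within 24 hours even without a clock time. Partial dates should be rarest in this window: patients are on site for imaging at 3 hours 50 minutes, and injection-site findings are recorded before dosing, at 15 minutes and at discharge. Any AE missed by the rule is known to follow randomisation, so it stays in the study-emergent tables and in the listings.

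All of this stands and limits the point, but it does not remove the mismatch. The 24-hour limb exists to catch events regardless of attribution, and that is the limb the date rule fails to protect. The before/after field does not say which injection is meant, or whether onset on another day was within 24 hours.

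A reader might infer more than the documents support:

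- *All AEs around the second injection are lost.* Only partially dated ones not assessed as related are affected, and they lose a flag, not their place in the data. The SAP states no exclusion; the omission follows from its silence together with no imputation.
- *Half to 70% of AEs around the first injection are missed.* The percentages are shares of patients in whom a month-only AE would be missed, not shares of AEs. The upper values assume injection at days 15 to 22, while earlier dosing is allowed.
- *About 240 patients are exposed to the second-injection gap.* That is 24% of half of 2001, a full-enrolment figure. The sponsor terminated the study early (SAP 2.4, section 6), and footnote f exempts patients who already have an ICD.
- *The rule is anti-conservative overall.* It also flags events that must precede dosing, so the net direction is not known.

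**Conclusion.** The mismatch is real and follows from the text of SAP 5.5.2 alone. The rule can err both ways: it misses partially dated, not-related AEs that may lie within 24 hours of an injection, and it flags some AEs that must precede the first one.

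The share of patients in whom a month-only date at the first injection would be missed runs from 23% to 72%, depending on the assumed lag. At the second injection, month-only and year-only dates are never caught by the rule. How many AEs this changes cannot be stated, because the documents do not give the number of partially dated AEs; it could be zero. The consequence is confined to the AdreView-emergent safety tables. It is a small point, worth correcting because the rule as stated misclassifies events and the second injection is given in one arm only.

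**What to change.** Split the rule in SAP 5.5.2:

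- **Study-emergent:** keep randomisation as the anchor. If the AE cannot be placed relative to randomisation, assume study-emergent.
- **AdreView-emergent:** assume emergent when the possible onset range overlaps the 24 hours after any AdreView administration, first or second, and cannot be excluded from it. Use the before/after-AdreView field where it narrows the range. Do not flag an AE whose latest possible date precedes the first administration. Leave the causality limb as it is.

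With this wording, every AE dated only to the month or year of an injection is tested against that injection, so the uncaught share falls to 0% for both.

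The cost is one SAP sentence and minor programming before database lock, which is when SAP section 1 requires sign-off. AdreView-emergent counts may move slightly in either direction.

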5.5.2.1 Overall Summary of Adverse Events

The number and percentage of patients experiencing AEs will be summarized, and p-values comparing the two study arms will be provided for the following AE categories:

- Any study-emergent AEs;
- Any serious study-emergent AEs;
- Any AdreView™-emergent AEs;
- Any serious AdreView™-emergent AEs;
- Any study-emergent AEs related to AdreView™;

- Any AdreView™-emergent AEs related to AdreView™;
- Any study-emergent AEs related to ICD implantation;
- Study-emergent AEs by maximum intensity;
- AdreView™-emergent AEs by maximum intensity;
- Any study-emergent AEs leading to discontinuation from the study;
- Any AdreView™-emergent AEs leading to discontinuation from the study;
- Any AdreView™-emergent AEs leading to death;
- Any study-emergent AEs leading to death.

In addition, number of AEs, number of study-emergent AEs, and number of AdreView™-emergent AEs will be provided.

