8 TREATMENT OF PATIENTS

8.1 Investigational Medicinal Product (IMP)

8.1.1 AdreView™ (Iobenguane I¹²³ Injection)

After randomisation to either the AdreView™ group or the SoC group, all patients will receive at least one intravenous injection of 10 mCi (370 MBq) of AdreView™. A $\pm 10\%$ tolerance of the nominal dose will be allowed, thus yielding an acceptable dose range of 9 to 11 mCi (333 to 407 MBq) in accordance with the Package Insert/Summary of Product Characteristics/Investigator's Brochure (IB). AdreView™ will be administered in a volume of 5 mL (diluted using 0.9% sodium chloride as needed) and injected as a slow infusion over 1 to 2 minutes followed by 10 mL of saline flush injected over a maximum of 5 seconds. An administration volume of up to 15 mL may be used at sites where there are logistical limitations to achieving delivery of IMP within the timelines required to meet the $370 \pm 10\%$ MBq dose in a volume of 5 mL.

Patients being allocated to the AdreView™ low-risk group will receive a second injection of AdreView™ and planar /SPECT imaging 2 years (± 30 days) after the first one. If any of these patients voluntarily withdraw prior to completion of the study they will be offered this second AdreView™ scan prior to withdrawal being effective.

Refer to the Package Insert/Summary of Product Characteristics/IB and Appendix [15.2](#) for further detail.

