12.2 Populations for Analysis

A patient is defined as having been included into the study if he/she has met all inclusion criteria, none of the exclusion criteria, and has been assigned to 1 of the enrolment groups (the AdreView™ group or the SoC group). The primary efficacy population is defined as those patients who were randomised to the AdreView™ group or the SoC group.

All randomised patients will be analysed for efficacy in the group to which they were randomised.

The safety population is defined as all patients who were enrolled in the study. All patients will be analysed for safety in the enrolment group to which they were assigned.

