4.1.1 Safety Analysis Set (Safety Population)

The safety analysis set comprises all patients who signed the informed consent form and met all of the inclusion criteria and none of the exclusion criteria.

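### AdreView-emergent AE percentages and between-arm p-values mix injection uptake with number of injections, so they do not estimate risk per injection

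*SAP*

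**What the plan says.** **Denominator.** SAP 4.1.1 defines a safety set that "comprises all patients who signed the informed consent form and met all of the inclusion criteria and none of the exclusion criteria". Protocol 12.2 words it differently: "The safety population is defined as all patients who were enrolled in the study". Neither requires an injection. SAP 5.5.1 then states: "All safety analyses will be performed by study arm in the safety population". No injected-only set is defined in either document.

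**Exposure.** Protocol 9.3 plans one injection in both arms: "AdreView™ will be administered to all patients". It follows randomisation; footnote f of the schedule in SAP 2.2 reads "First AdreView™ administration should be performed in the 15 (+7) days post-randomisation". Protocol 8.1.1 adds a repeat dose for one subgroup: "Patients being allocated to the AdreView™ low-risk group will receive a second injection of AdreView™". That injection is due at 2 years. Under the same footnote, withdrawal or an earlier ICD can alter or remove it.

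**Event definition.** Under SAP 5.5.2, an AE is AdreView-emergent if it starts or worsens within 24 hours of an administration, whatever its cause, or later if the investigator assumes a causal link. An AE that cannot be dated relative to randomisation is also counted as AdreView-emergent, with no check that an injection was given.

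**Presentation.** SAP 5.5.2.1 says that "p-values comparing the two study arms will be provided for the following AE categories"; it lists 13 categories and names no test. No AE table is split by administration, although SAP 5.3 summarises dose and volume for each one.

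**The concern.** A reader will take the AdreView-emergent rows as the safety profile of the injection. Three features stand in the way.

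- A patient can be in the denominator without having been injected, which lowers the percentage.
- A re-injected patient has two 24-hour windows in which any AE counts, related or not. Even a harmless injection would then produce an excess in the AdreView arm.
- The p-value compares two arms that receive the same product at the same dose. If nobody is re-injected and uptake is equal, the expected difference is zero however risky the product is.

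Without a split by administration, the planned tables also cannot show whether the repeat injection carries a different AE rate. That question arises only for the AdreView low-risk group.

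**Working it through.** **Inputs**

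- Low-risk share (H/M ≥ 1.6): 24%, from SAP 2.3. It reproduces from the same section: 21% and 25% in the two LVEF bands, mixed 1:4, give (1×21 + 4×25)/5 = 24.2%.
- Arm size: 2001 patients randomised 1:1, about 1000 per arm. This is the full planned size.
- Risk per injection, p: 1.3% as an illustration, the injection-site reaction frequency in protocol 10.2.10. The emergent definition also counts unrelated AEs within 24 hours, so 5% and 10% are shown as assumed values.
- Share f of low-risk patients actually re-injected, and share u of patients never injected: not given, so ranges are used.
- Significance threshold: two-sided 0.05, SAP section 5.

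**Injections per patient.** SoC: 1.00. AdreView arm: 1 + 0.24f, which is 1.24 at f = 1, 1.12 at f = 0.5 and 1.00 at f = 0.

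**Share with any emergent AE**, assuming the same risk at every injection and independence between injections:

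- SoC: p
- AdreView: (1 − 0.24f)p + 0.24f[1 − (1 − p)²]

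At p = 1.3% and f = 1: 0.76 × 0.013 + 0.24 × (1 − 0.987²) = 0.00988 + 0.24 × 0.025831 = 0.01608. That is 1.61% against 1.30%, a ratio of 1.24 and a difference of about 3 patients per 1000. At f = 0.5 it is 1.45% against 1.30%, ratio 1.12.

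**Chance of p < 0.05 when the risk per injection is identical in both arms.** With d the difference in proportions and SE its standard error at 1000 per arm, the chance is Φ(d/SE − 1.96) + Φ(−d/SE − 1.96). This assumes a two-sample comparison of proportions.

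| Risk per injection | None re-injected | Half of low-risk | All low-risk |
|---|---|---|---|
| 1.3% | 5% | 6% | 9% |
| 5% | 5% | 9% | 20% |
| 10% | 5% | 12% | 34% |

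**Insensitivity to product risk.** With f = 0, raising p tenfold from 1.3% to 13% leaves the expected between-arm difference at 0.

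**Dilution by uninjected patients.** Ignoring undatable AEs, the reported share is (1 − u)p. A true 1.3% becomes 1.29%, 1.24%, 1.17% or 1.04% at u = 1%, 5%, 10% or 20% (assumed range). If u differs by arm, for example 2% in AdreView and 10% in SoC (assumed), the ratio is 0.98/0.90 = 1.09 with no re-injection and 1.35 with full re-injection. With 10% in AdreView and 5% in SoC and no re-injection, it is 0.90/0.95 = 0.95.

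**The case against.** The strongest reply is that the second scan belongs to the AdreView-guided strategy (protocol 9.5), and protocol 10.1.4 describes the trial as a comparison of two strategies. Extra injections, and any AEs that follow, are a real consequence of randomisation to that arm. This stands: a by-arm count is a legitimate description of strategy burden. What it does not provide is risk per injection, and the SAP does not claim that it does.

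Other parts of the reply also stand.

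- The p-values appear only in the overall summary. SAP 5.5.2.2 makes the system organ class and preferred term tables the primary AE presentation, with no p-values planned there. No decision rule uses them. The denominator issue does reach those tables.
- Injection is planned for everyone. Early termination alone would stop a first injection only in patients not yet scanned within the 15 (+7) day window.
- AdreView-emergent events are flagged in listings, and injection-site findings are recorded at both administrations. The information exists; what is missing is a summary by administration.
- SoC patients are due one injection each, so apart from uninjected patients and undatable AEs, the SoC column does estimate first-injection risk.

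A reader might infer that uninjected patients can never contribute an event, so that rates are always understated. The documents do not support that: the undatable-AE rule can put an uninjected patient in the numerator.

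**Conclusion.** The point holds as a minor safety-reporting issue. As planned, the AdreView-emergent percentages and p-values mix uptake with number of injections and do not estimate risk per injection. The planned ceiling is about 1.24 against 1.00 injections per patient, or 1.61% against 1.30% at the illustrative 1.3%, assuming equal and independent risk per injection and re-injection of all low-risk patients. Death, withdrawal, an earlier ICD and early termination lower it. The size of the dilution is unknown because the uninjected share is not given; at a few per cent it is small.

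A reader might infer a 24% inflation in the actual results, or an invalid safety comparison overall. Neither follows. The 24% is a planning maximum, and the larger chances of p < 0.05 need both full re-injection and risks of 5% to 10% at full planned arm size. The comparisons of study-emergent AEs, apart from the category related to AdreView, and of ICD-related AEs remain meaningful. The primary endpoint is untouched.

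It may also be tempting to keep a between-arm p-value restricted to the first administration. With the same product and dose in both arms, that test would say nothing about product risk.

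**What to change.** In SAP 5.5.2 and its subsections, for AdreView-emergent AE and SAE tables and for AEs related to AdreView:

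1. Use as denominator the patients who received the administration in question.
2. Show the first administration by arm and pooled, and the second administration (AdreView low-risk patients) separately.
3. Drop the between-arm p-values for these categories.
4. Apply the undatable-AE assumption only to patients with a recorded injection.
5. In re-injected patients, assign a late causally related AE to the most recent administration before onset. The relationship categories in SAP 5.5.2.4 do not say which administration is meant.

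Leave the between-arm comparisons of the other study-emergent AEs and of ICD-related AEs in place.

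The cost is SAP wording and minor programming: an exposure flag per administration plus the attribution rule. No new data are needed. Protocol 8.6 covers the date and time of administration, and the 24-hour definition already depends on them. The reported AdreView-emergent percentages may come out slightly higher.
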